    - (a) Baseline (15 minutes post-exam) blood pressure readings (three left arm seated readings, average will be calculated) and one heart rate reading taken after at least 5 minutes of rest time without talking, eating, or caffeine consumption.
    - (b) 15 minutes after examination – will be given 1/8 tsp (900mg) of *Passiflora incarnata* solid extract by Wise Woman Herbals mixed with 1/8 tsp of blackstrap molasses to mask the taste and a 10 minute audio-guided mobile meditation session via the Headspace App. Subjects may not consume caffeine or eat food during this time.
    - (c) Three left arm seated blood pressure readings and one heart rate will be taken 15 minutes after the baseline reading.

UB HRP-503 TEMPLATE: Protocol

PROTOCOL TITLE: Investigating the short-term effects of *Passiflora incarnata* and mobile audio-guided meditation on blood pressure and heart rate in naturopathic medical students

PROTOCOL DATE: 3/28/19

Template Revised: June 14, 2010

vii) Safety considerations

- (1) All participants will be given a paper survey about adverse events (*see Attachment C*) which will be returned to the research team by the end of the same study day. Any participant who marks a moderate-severe adverse event will be followed up by [name] for appropriate management.
- (2) [name] phone number and contact information will be given to the study subjects so they can contact her in the event another adverse event arises after the survey has been returned.
- (3) The research will last for about 45 minutes. Three Blood pressure readings (all left arm seated) and one heart rate reading will be taken at baseline and again 15 minutes later.
- (4) Procedures taken to lessen the probability or magnitude of risks
  - (a) Adverse events related to *Passiflora incarnata* use have been found with chronic dosage. We attempt to minimize these risks by providing one-time acute dosage.
  - (b) We are attempting to minimize adverse events by excluding participants who are taking hypertensive medication, anti-anxiety medication, MAOI medication, or blood-thinning medication.
  - (c) We are attempting to minimize adverse events by excluding participants who are pregnant or may be pregnant.

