- i) [name] will evaluate the adverse events survey and follow up with any participant who experience a moderate-severe adverse event
  - ii) Participants will be encouraged to report additional adverse events to [name] directly in the days following the research even once the survey has been handed in.
- g) Withdrawal of subjects\***
- i) Participants can voluntarily withdraw at any time
  - ii) Once a participant has withdrawn from the research, his/her data will not be included in our analysis
  - iii) Withdrawal may occur without the participants' consent if:
    - (1) His/Her smartphone or Headspace application is not functioning within 30 minutes after the end of his/her classroom examination
    - (2) He/She did not take the classroom examination that day
    - (3) He/She eats food/tyramine containing food, stimulant medication, alcoholic beverages, cold medicine, decongestant medication, antihistamine medication, cough suppressant medication, stimulant energy drinks, or consume caffeine within 2 hours before the study period or during the study period.
- 7) Risks to subjects\***
- a) Privacy Risks**
- i) Since naturopathic medical students will be studied in groups in one large room, the subjects will be informed that his/her classmates in the same room will know that he/she is participating in the study.
  - b) To minimize any privacy risks, all medical information will be collected in private before the day of the study. On the day of the study, we will not read the participants' blood pressure and heart rate readings out loud. We also will ask the participant to write down what medications or drinks taken on the day of the study

UB HRP-503 TEMPLATE: Protocol

PROTOCOL TITLE: Investigating the short-term effects of *Passiflora incarnata* and mobile audio-guided meditation on blood pressure and heart rate in naturopathic medical students

PROTOCOL DATE: 3/28/19

Template Revised: June 14, 2010

so that the participant does not have to say this information out loud in order to protect privacy.

- c) **Inconveniences: Time Invested/Timing with Classroom Examination**
  - i) The participants may be inconvenienced by sparing 45 minutes after his/her classroom examination
  - ii) The participant may feel distracted during his/her examination in anticipation of the research taking place after the examination
    - (1) This is unlikely, as the research is intended to have a relaxing benefit on the participant

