- (1) Drowsiness (very common, up to 50% reported this adverse effect in studies). Due to this very common side effect, we advise the subject to exercise caution and avoid operating a vehicle or heavy machinery for one hour after taking the dose.
- (2) Muscle relaxation (common, up to 20% reported this in studies). Due to this very common side effect, we advise the subject to exercise caution and avoid operating a vehicle or heavy machinery for one hour after taking the dose.
- (3) Dizziness (common, up to 5% reported this in studies). Due to this very common side effect, we advise the subject to exercise caution and avoid operating a vehicle or heavy machinery for one hour after taking the dose
- (4) Headache
- (5) Abdominal Pain
- (6) Flatulence
- (7) Vasculitis (rare)
- (8) Asthma
- (9) Rhinitis
- (10) Urticaria/Allergic Reaction
- (11) Cardiovascular effects, including Ventricular Tachycardia (one case study, rare)
- (12) Uterine contractions
- (13) Nosebleed, blood-thinning
- (14) Impairment of Job Performance
- (15) Confusion
- (16) Ataxia
- (17) Other unforeseeable adverse reactions

iii) Our exclusion criteria is intended to reduce the risk of adverse events. Our study will involve a one-time acute dosing of *Passiflora incarnata* to reduce the risk of adverse events from chronic, long-term usage.

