## 8) Potential benefits to subjects\*

### a) Relaxation

- i) *Passiflora incarnata* has been found to have anxiolytic properties and might reduce sympathetic tone. The participants may note a sense of well-being and relaxation after participating in the research
- ii) Meditation has been found to improve well-being in medical students. The participants may note an improved sense of well-being and sense of relaxation after participating in the research
- iii) These relaxation effects are likely and should last for the rest of the research day

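### Does the one-hour driving caution contradict the statement that relaxation lasts for the rest of the research day?

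*Protocol*

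**What the plan says.** Section 7(f)(ii) of the protocol lists 17 possible adverse effects of Passiflora. The first three, drowsiness (up to 50%), muscle relaxation (up to 20%) and dizziness (up to 5%), are the only ones with a rate. Each carries the same advice: "we advise the subject to exercise caution and avoid operating a vehicle or heavy machinery for one hour after taking the dose". The sentence that introduces the list attributes the effects to use over weeks to months.

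Section 8(a) sets out the benefits. Item (i) says that Passiflora "has been found to have anxiolytic properties and might reduce sympathetic tone" and that participants may notice a sense of well-being and relaxation. Item (ii) says much the same of meditation. Item (iii) then covers both: "These relaxation effects are likely and should last for the rest of the research day".

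Two other places bear on the point. Section 6(d)(vii)(4)(a) links adverse events to chronic dosing and adds: "We attempt to minimize these risks by providing one-time acute dosage". Section 3 describes a dental-extraction trial of one 260 mg preoperative dose, in which 50% of participants had drowsiness, 20% muscle relaxation and 5% dizziness.

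**The concern.** On a first reading, the same dose has a one-hour effect where it is a risk and an all-day effect where it is a benefit. The word relaxation appears on both sides, as an adverse effect in section 7 and as a benefit in section 8. The protocol gives no basis for either period, and section 3 gives no duration for any effect.

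If the two statements did concern the same effect, one of them would have to give way. Either the caution would end while the effect continued, or the ethics board would be weighing an overstated benefit. Subjects leave before the hour is over, so the last part of the caution is theirs to follow unsupervised.

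The chronic-use framing of the risk list adds to the unease. One-time dosing is offered as the way to reduce risk, although the three most frequent listed effects were seen after a single dose.

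**Working it through.** **Rates.** The risk list in section 7(f)(ii) against the single-dose trial in section 3:

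| Effect | Section 7(f)(ii) | Section 3, one 260 mg dose |
|---|---|---|
| Drowsiness | up to 50% | 50% |
| Muscle relaxation | up to 20% | 20% |
| Dizziness | up to 5% | 5% |

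All three agree exactly, so they are acute, single-dose rates. The introduction to the list and the rationale in 6(d)(vii)(4)(a) do not describe them correctly. Section 7(f)(iii) does not have this fault, because it limits its claim to risk from long-term use.

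**Clock.** Set the end of the exam at 0.

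- Group III is dosed "15 minutes after examination" (section 6(d)(vi)(3)(b)), so the dose is at 15 min.
- The caution ends at 15 + 60 = 75 min.
- Section 7(c)(i) says "The participants may be inconvenienced by sparing 45 minutes after his/her classroom examination". On that reading subjects leave at 45 min, which is 45 − 15 = 30 min after the dose, and 75 − 45 = 30 min of the caution remain.
- Section 6(d)(vii)(3) says only that the research lasts about 45 minutes. If that runs from the baseline reading, subjects leave at 15 + 45 = 60 min, and 75 − 60 = 15 min remain.

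**Gap to the end of the day.** If T is the time in hours from the end of the exam to the end of the research day, the time after the caution lapses is T − 1.25. The protocol does not give T. Assuming T between 2 and 6 h, the gap runs from 2 − 1.25 = 0.75 h to 6 − 1.25 = 4.75 h. This measures only the time left in the day once the caution has ended. It does not measure time spent drowsy or dizzy, because no duration is given for those effects.

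**Do the two statements share a subject?**

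| | Section 7(f)(ii)(1)–(3) | Section 8(a)(iii) |
|---|---|---|
| Kind of statement | advice about an activity | expected duration of a benefit |
| Effects | drowsiness, muscle relaxation, dizziness | sense of well-being and relaxation |
| Attributed to | Passiflora | Passiflora and meditation jointly |
| Who it covers | subjects given Passiflora (Group III) | any meditating subject, including Group II on placebo |

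They differ on every row. A limit on driving does not say how long a feeling of calm lasts. A feeling of calm that lasts all day does not show that drowsiness or dizziness does. A contradiction would need a sentence that gives both durations to the same effect, and the protocol has none.

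**The case for a change.** The strongest argument for acting is that section 8(a)(iii) is the protocol's only explicit statement of how long any effect lasts. It refers back to Passiflora as well as to meditation, and it outlasts the only caution period without explanation. An ethics board could fairly ask for the basis of each period. That stands, but it is a request for detail. It does not show that either period is wrong, and because the benefit is stated jointly with meditation, no Passiflora-specific duration can be read out of it.

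The second argument is firmer: the chronic-use wording in 7(f)(ii) and 6(d)(vii)(4)(a) disagrees with section 3 for the three effects that carry rates. The same single-dose trial also reported allergy and epistaxis, at 2.5% each. The disagreement is real. It is a slip of description, though, and does not hide the acute risk. The three rates are shown in full, and the advice beside them is timed from taking the dose, so a reader is not led to think that one dose is free of these effects.

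The timing argument also has some force, since 15 to 30 of the 60 caution minutes fall after subjects leave. But the advice is written to be followed after the session. The adverse event survey is due by the end of the study day, and section 6(f)(ii) invites further reports in the days that follow. Safety reporting therefore does not stop when the hour ends.

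**Conclusion.** The contradiction does not hold. The one-hour advice and the all-day benefit concern different effects, and the benefit is only partly attributed to Passiflora. At most the difference is unexplained. Its size cannot be calculated from the protocol: 0.75 to 4.75 h follows only from assuming T between 2 and 6 h.

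What remains is a clerical inaccuracy in two phrases, the introduction to 7(f)(ii) and the rationale in 6(d)(vii)(4)(a). Both speak of prolonged use, while all three rates in the list come from a single-dose trial. The authors could tidy this at any later revision. It changes nothing that is done to subjects, measured, analysed or concluded, because the rates, the caution from dosing and the same-day survey are already in place.

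This view rests on reading section 8(a) as describing a subjective state, which is how its items (i) and (ii) put it. The consent text was not available, so the exact words given to subjects are not judged. No view is taken on how long any caution should last.

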## 6) Study Design

### a) Recruitment Methods

- i) We will recruit from the naturopathic medical program, which currently has 77 enrolled students.
- ii) A flyer will be posted and emailed out to the naturopathic student body (*see Attachment A*)
- iii) Naturopathic student participants will NOT be recruited during class time with [name] or [name] to reduce any conflict of interest or feeling of persuasion that the student may have.
- iv) All naturopathic students will be invited to participate. Once a student expresses interest, he/she will be given the inclusion/exclusion criteria checklist (*see Attachment B*) to ensure eligibility.
  - (1) Exclusion criteria: Those taking hypertensive, blood-thinning, or anti-anxiety medications (including MAOI medications), those with surgery in the past 2 weeks or coming in the next 2 weeks, those females who are currently pregnant or could be pregnant
    - (a) “Day Of” exclusion criteria: consuming food, caffeine, use of stimulant medication, use of MAOI medication, alcoholic beverages, consumption of tyramine containing foods (i.e. blue cheese, gorgonzola cheese, red wine, cured meat, cured fish, sauerkraut, sourdough bread, soy sauce, teriyaki sauce, miso tempeh, or overripe fruits), consumption of cold medicine, antihistamine medication,

UB HRP-503 TEMPLATE: Protocol

PROTOCOL TITLE: Investigating the short-term effects of *Passiflora incarnata* and mobile audio-guided meditation on blood pressure and heart rate in naturopathic medical students

PROTOCOL DATE: 3/28/19

Template Revised: June 14, 2010

decongestant medication, cough suppressant medication, or use of stimulant energy drinks within 2 hours before the study period.

(2) Participants will not be given any incentive to participate (i.e. no payment or “extra credit” will be given).

v) Interested participants will be screened for eligibility (see Attachment B) and allowed to participate if they do not meet any of the exclusion criteria

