**b) Inclusion and Exclusion Criteria\***

i) **Inclusion criteria** – all naturopathic medical students are invited to participate

(1) Participants must have a smartphone with access to the Headspace application and headphones to listen to the session

ii) **Exclusion criteria**

(1) Those taking hypertensive medication

(2) Those taking anti-anxiety medication, including MAOI medication

(3) Those taking blood-thinning medication

(4) Those who are pregnant

(5) Those who could be pregnant

(6) Those who will have surgery 2 weeks before the research date

(7) Those who are scheduled to have surgery 2 weeks after the research date

(8) Those who do not have a smartphone or access to Headspace application

(9) Those who have consumed caffeine, food/tyramine containing foods, stimulant medication, cold medicine, decongestant medicine, antihistamine medicine, cough suppressants, alcoholic beverages, or stimulant energy drinks within 2 hours before the study period.

iii) Interested participants will be contacted by phone or in-person by one of the investigators ([name] or [name]) and screened for exclusion criteria

iv) We aim for 70 subjects to participate but can complete the research with 45-60 subjects to achieve 80-90% power, respectively.

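### Current passionflower use is not an exclusion criterion, so on the text shown a student taking it, at least for a reason other than anxiety, can enter any arm

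*Protocol*

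**What the plan says.** Section 7(f)(iii) offers two protections against harm from the extract. The first is eligibility: "Our exclusion criteria is intended to reduce the risk of adverse events". The second is single dosing, chosen "to reduce the risk of adverse events from chronic, long-term usage". Section 6(d)(vii)(4)(a) says the same of single dosing: "We attempt to minimize these risks by providing one-time acute dosage". Item (b) there spells out the eligibility part: "We are attempting to minimize adverse events by excluding participants who are taking hypertensive medication, anti-anxiety medication, MAOI medication, or blood-thinning medication".

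The operative lists are these:

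- **6(a)(iv)(1):** "Those taking hypertensive, blood-thinning, or anti-anxiety medications (including MAOI medications"), with surgery and pregnancy.
- **6(b)(ii):** the same classes as separate items, among them "Those taking anti-anxiety medication, including MAOI medication" and "Those taking blood-thinning medication", plus lack of a smartphone or the app.
- **Day-of items in 6(a)(iv)(1)(a) and 6(b)(ii)(9), and the withdrawal list in 6(g)(iii)(3):** food, tyramine foods, caffeine, alcohol, energy drinks, stimulants and cold-type remedies, within two hours of the study period.

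Under 6(a)(v), screened students are "allowed to participate if they do not meet any of the exclusion criteria". Section 6(d)(vii)(5)(b) collects medication use on a questionnaire. Sections 7(b) and 9(f) have participants write down that day's medications and drinks.

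**The concern.** No list names Passiflora, and none mentions botanicals or supplements. Yet the protocol's own reasons for excluding two of the drug classes apply to the test plant. Section 3 describes it as a herb long used against anxiety, and credits it with a possible antiplatelet effect. The participants are naturopathic students studied on an examination day, so some use of a calming herb is plausible, although the protocol gives no rate.

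Two things are at stake. For a user allocated to Group III, the study dose comes on top of exposure that the protocol has neither excluded nor clearly arranged to record. For a user in Group I or II, a participant meant to be free of Passiflora is not. The contrast most affected is Group III against Group II, since both receive the meditation and only that comparison isolates the extract.

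**Working it through.** The main check is textual. It takes a student who currently uses passionflower through the rules in order.

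1. **Standing criteria, 6(a)(iv)(1) and 6(b)(ii).** If the student takes it for anxiety, a screener may count it as anti-anxiety medication. The text does not say so, and MAOI is the only class it spells out. If the student takes it for another reason, no item clearly applies.
2. **Day-of items, 6(a)(iv)(1)(a) and 6(b)(ii)(9).** The two-hour ban on food would catch Passiflora eaten as food in that window. It would not catch a passionflower drink, or use earlier that day or habitually.
3. **Admission rule, 6(a)(v).** A student who meets no criterion may take part.
4. **Allocation, 6(d)(ii) and (vi).** The student is randomised to Group I, II or III, so any arm is possible.
5. **Records.** A questionnaire on medication, or a slip listing medications and drinks, may reveal the use. No listed criterion then acts on it.

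**Effect on the comparison.** Randomisation spreads prior users across arms by chance, so there is no systematic imbalance. The readings are taken at baseline and 15 minutes later, and an effect already present sits largely in both. What remains is dilution of the contrast. Its size needs the share of users, which the protocol does not give.

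**Cost of excluding users.** Inputs: 77 enrolled students (section 5), a target of 70, and 45-60 stated as enough for 80-90% power (6(b)(iv)). The target already needs 70/77 = 90.9% of the pool. The number that can be lost before each figure is out of reach:

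- 70: 77 − 70 = 7 students (9.1%)
- 60: 77 − 60 = 17 students (22.1%)
- 45: 77 − 45 = 32 students (41.6%)

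Existing exclusions draw on the same margin. If the three student research assistants are among the 77 and do not take part (an assumption), the margins are 74 − 70 = 4, 74 − 60 = 14 and 74 − 45 = 29.

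The share lost is unknown, so the table uses an assumed range:

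| Assumed loss | Students left | Participation needed for 45 | For 60 | For 70 |
|---|---|---|---|---|
| 5% (4) | 73 | 45/73 = 61.6% | 60/73 = 82.2% | 70/73 = 95.9% |
| 10% (8) | 69 | 45/69 = 65.2% | 60/69 = 87.0% | not possible |
| 20% (15) | 62 | 45/62 = 72.6% | 60/62 = 96.8% | not possible |
| 30% (23) | 54 | 45/54 = 83.3% | not possible | not possible |

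The lower figure of 45 stays within reach throughout this range. The target of 70 does not survive a 10% loss.

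**The case against.** The strongest reply is that the gap may be narrower than it looks. Screening uses Attachment B and medication use is taken on Attachment D. Neither is shown, and either may ask about supplements. Screening is done by investigators, who may well treat passionflower taken for anxiety as anti-anxiety medication. Both points stand. They are why the claim is limited to the text shown and is firmest for use for other reasons. They do not remove it, because the written criteria would still be silent on the test plant.

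Three stronger readings are tempting, and the document does not support them.

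- **That the single-dose safeguard fails.** The study still gives one dose. A habitual user's chronic exposure exists with or without the trial, and nothing in the protocol shows that one added dose is more dangerous for that person. The statement that the criteria are meant to reduce risk is not false.
- **That the dose shows the size of the hazard.** The 900 mg dose exceeds the 260-700 mg that section 3 gives for earlier trials. That applies to every Group III participant, user or not, and preparations may differ in strength.
- **That power is materially lost or the comparison biased.** Any power figure needs an assumed share of users, and also that a control's change score already carries the treatment effect. With a baseline reading, much of an existing effect cancels.

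It is also fair to object that excluding every botanical taken for blood pressure, anxiety or blood thinning goes beyond the gap, in a pool where the target already needs 91% participation. That objection is accepted.

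**Conclusion.** The point holds in a limited form. As written, the eligibility rules do not name Passiflora, so a current user, at least one taking it for a reason other than anxiety, can be enrolled in any arm. In Group III this adds the study dose to existing exposure. In Groups I and II it exposes a control to the test plant, with a dilution that is probably small and cannot be quantified from the protocol. It is a cheap improvement and does not threaten the trial's conclusions.

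The conclusion rests on the text shown. If Attachment B already screens out passionflower users, all that is left is to bring 6(a) and 6(b) into line with it.

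**What to change.** 1. In 6(a)(iv)(1), 6(b)(ii) and the Attachment B checklist, add as a standing criterion: *current use of any Passiflora product, for any reason*, within a look-back window set by the investigator. Apply it at the private screen, before randomisation.
2. Record other botanical and supplement use in the baseline questionnaire (6(d)(vii)(5)(b)) and on the day-of slip (7(b), 9(f)), unless the attachments already ask. Do not exclude for it.
3. Do not add these items to the withdrawal list in 6(g)(iii)(3). Students are randomised before the study begins (6(d)(ii)), and 6(g)(ii) drops the data of anyone withdrawn. More withdrawal triggers would mean more exclusions after randomisation, a worse problem than the dilution they would prevent. Passionflower use that comes to light on the day should be recorded.

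Recording is a change of wording only. The exclusion costs an unknown but probably small number of the 77 students. The target of 70 has little slack, but the stated sufficient range of 45-60 has more.
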